7.5 Procedures for Apple Watch wear

Participants will be asked to wear their Apple Watch as they would with normal use.

Participants with a Series 4 Apple Watch will be asked to take an ECG at least 2 times each day while wearing the ECG patch. In addition, participants will be asked to take an ECG app recording after receiving each irregular rhythm notification.

7.6 Procedures for Study Visit #2

Once the ePatch has been received by BioTelemetry and the final report has been adjudicated, BioTelemetry will issue a notification to the Study Telehealth Provider. The participant will be notified by way of a secure email that their patch report is ready and will be instructed to contact the Study Telehealth Provider for Study Visit #2 through a button in the app. It is expected that this visit will occur between 15-45 days after enrollment, depending on timing of ambulatory ECG monitor wear, mailing, and interpretation.

The Study Telehealth Provider will review the ambulatory ECG monitoring report with the participant and make any necessary recommendations to the participant. The Study Telehealth Provider will then refer participants with AF, any clinically relevant cardiac arrhythmias, or any non-urgent symptoms requiring follow up detected on patch monitoring to their primary health care provider for further treatment and diagnostic testing. For participants without established primary health care providers, the Study Telehealth Provider will offer referral per standard Study Telehealth Provider protocols. The ambulatory ECG monitoring report and visit summary will be made available to the participant and also to participant's physician or health care provider, if the participant provides the Study Telehealth Provider information of participant's physician and permission to send that physician a copy of the report. Any referral

This document contains information that is privileged or confidential and may not be disclosed unless such disclosure is required by applicable laws and regulations. The information in this document is the property of Apple Inc. and may not be reproduced, published, or disclosed to others without written authorization from Apple Inc.

visits will be conducted outside of the study, at the discretion of the participant, and at the cost of the participant.

Symptoms, disposition recommendations, and any adverse events reported will be logged.

7.7 Study Telehealth Provider Additional Visits

Participants may contact the Study Telehealth Provider through a button in the app outside of the scheduled study visits if they have symptoms concerning for arrhythmia that they wish to discuss with a provider, or questions/concerns about the study. The Study Telehealth Provider will review the participant's symptoms and refer participants to emergency medical services or their primary health care provider. Visits, symptoms, and any adverse events reported will be logged.

7.8 PRO Instruments at 15 and 60 days

Participants will be notified by the app to complete the 15 and 60-day PRO questionnaires at 15 and 60 days following enrollment. The questionnaires will be administered through a web-based survey, and the participant will have 30 days, up until END OF ENROLLMENT + 90, to complete them. Participants will receive reminders via notifications from the app to complete the PRO questionnaires. Questions will ask if the participant followed up with the Study Telehealth Provider and/or a non-study health care provider, received an AF diagnosis, was evaluated in-person by a non-study health care provider, the type of non-study health care provider and/or specialists, received additional cardiac testing, received other clinical arrhythmia diagnoses, anxiety as a result of participation, health status, and experience with the IRN feature and ECG app.

This document contains information that is privileged or confidential and may not be disclosed unless such disclosure is required by applicable laws and regulations. The information in this document is the property of Apple Inc. and may not be reproduced, published, or disclosed to others without written authorization from Apple Inc.

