2.2 Study Objectives

1a. To measure the proportion of participants with an Irregular Rhythm Notification (IRN) prior to enrollment who have atrial fibrillation or atrial flutter (AF) confirmed by ambulatory electrocardiographic (ECG) patch monitoring.

1b. To measure the proportion of participants with an ECG app classification of Atrial Fibrillation (ECG app-AFib) prior to enrollment who have AF confirmed by ambulatory ECG patch monitoring.

2a. To measure the proportion of participants who receive an IRN or ECG app-AFib reporting contact with a non-study healthcare provider at 15 and 60 days after study enrollment.

2b. To measure the proportion of participants with an ECG app classification of inconclusive prior to enrollment who have AF confirmed by ambulatory ECG patch monitoring.

2c. To measure the proportion of participants who have AF confirmed by ambulatory ECG patch monitoring by age at enrollment (< 65 and 65+).

This document contains information that is privileged or confidential and may not be disclosed unless such disclosure is required by applicable laws and regulations. The information in this document is the property of Apple Inc. and may not be reproduced, published, or disclosed to others without written authorization from Apple Inc.

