A second study visit, Study Visit #2, will occur with the Study Telehealth Provider once the ambulatory ECG monitor results are available. After the final ambulatory ECG monitor report is made available to the Study Telehealth Provider, the Study Telehealth Provider will contact the participant to prompt them to complete Study Visit #2. During Study Visit #2 (voice or video), the ambulatory ECG monitor results will be reviewed. If AF or any other arrhythmias have been detected in reviewing the ambulatory ECG monitor data, or if there are other non-urgent symptoms needing further evaluation, the Study Telehealth Provider will direct the participant to their primary health care provider, or other health care provider as deemed appropriate by the Study Telehealth Provider. The report and visit summary will be made available to the participant and also to participant's physician or health care provider, if the participant provides his/her physician information and permission to send that physician a copy of the report. For participants who do not have an established primary health care provider, the Study Telehealth Provider will encourage and offer advice in establishing a primary care provider per standard Study Telehealth Provider protocol.

Patient Reported Outcomes (PROs)

Fifteen and sixty days after enrollment, participants will receive a separate app notification to complete the patient reported outcomes (PRO) questionnaires. The participant will be notified about the sixty day questionnaire even if the participant does not complete the fifteen day questionnaire. These outcomes will include whether or not the participant contacted a primary health care provider and what additional treatments or diagnostic tests they underwent. They will also be asked questions related to measures of anxiety about testing, experience with the IRN feature and ECG app, and health status. Participants will receive reminders via notifications from the app to complete the PROs prior to the due date (within 30 days of notification).

This document contains information that is privileged or confidential and may not be disclosed unless such disclosure is required by applicable laws and regulations. The information in this document is the property of Apple Inc. and may not be reproduced, published, or disclosed to others without written authorization from Apple Inc.

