7.1 Eligibility Determination and Enrollment

The potential participant will first download the Apple Heart Study 1.2 App. The app will automatically ensure compatibility with the iPhone iOS version and Watch version. If compatible, the participant will be able to continue forward in the app. An overview of the study will be displayed in the app.

The participant will then advance to a screen for study enrollment, where they will confirm whether they meet general participation requirements. The participant will be asked questions based on study inclusion and exclusion criteria. The app will automatically determine eligibility based on the responses provided. If the participant is determined to be eligible, they will initiate the consenting process with an in-app consent and authorization form to be read and signed if they agree to participate.

Participants will be able to enroll between STUDY START DATE and END OF ENROLLMENT (STUDY START DATE + 6 months).

On END OF ENROLLMENT, enrollment will close. The study period will end on END OF ENROLLMENT + 60.

A 15-day PRO will become available 15 days after enrollment, no later than END OF ENROLLMENT + 15. A 60-day PRO will become available 60 days after enrollment, no later than END OF ENROLLMENT + 60. All PROs will be due by end of study on END OF ENROLLMENT + 90. After this date, all monitoring will end, the Study Telehealth Provider line will be closed and no further data will be collected.

This document contains information that is privileged or confidential and may not be disclosed unless such disclosure is required by applicable laws and regulations. The information in this document is the property of Apple Inc. and may not be reproduced, published, or disclosed to others without written authorization from Apple Inc.

Enrollment may be terminated early if more than 400 participants receiving an IRN and more than 400 participants using the ECG app are diagnosed with AF by ECG patch. Enrollment will be reviewed at STUDY START DATE + 60 days. If enrollment in each of the study subgroups outlined in the objectives appears that it will not achieve a sufficient number of subjects to meet study goals, we will enhance recruitment by targeting recruitment strategies to the group(s) of participants at risk for failing to meet study goals or extend the duration of enrollment.

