4.3 Analysis Methods

Analysis of the Primary Endpoint Addressing Objective 1a and 1b

For Objectives 1a and 1b we have designed the study to estimate the proportion of participants diagnosed with AF within a 0.10 confidence interval width.

Objective 1a – The proportion of participants with an IRN prior to enrollment who have AF confirmed by ambulatory ECG patch monitoring.

This proportion will be estimated as the ratio of the number of participants in the EAS who have atrial fibrillation or atrial flutter of at least 30 seconds duration on patch wear and received an IRN before enrollment, divided by the number of participants in the EAS who received an IRN before enrollment. An exact 95% two-sided confidence interval will also be presented. We will also describe the number of participants who received an IRN before or during enrollment with arrhythmias other than atrial fibrillation.

Objective 1b Analysis – The proportion of participants with an ECG app-AFib classification prior to enrollment who have AF confirmed by ambulatory ECG patch monitoring.

This proportion will be estimated as the ratio of the number of participants in the EAS who have atrial fibrillation or atrial flutter of at least 30 seconds duration on patch wear and received an ECG app-AFib classification before enrollment divided by the number of participants in the EAS who received an ECG app-AFib classification before enrollment. An exact 95% two-sided confidence interval will also be presented. We will also describe the number of participants who received an ECG app-Fib before enrollment with arrhythmias other than atrial fibrillation.

Analysis of the Secondary Endpoints Addressing Objectives 2a, 2b and 2c

Objective 2a Analysis - The proportion of participants with an IRN or ECG app-AFib classification reporting contact with a non-study healthcare provider at 15 and 60 days after study enrollment.

This proportion will be estimated as the ratio of the number of participants who received an IRN or ECG app-AFib classification in the EEAS who reported contact with a non-study healthcare provider at 15 (and separately at 60) days after study enrollment divided by the number of participants in the EEAS who received an IRN or ECG app-AFib. An exact 95% two-sided confidence interval will also be presented.

Objective 2b Analysis

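### The 15-day provider-contact proportion (Objective 2a) counts contacts made up to day 45, including those prompted by the Visit #2 referral, because neither the contact nor the response is dated

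*Combined protocol and SAP*

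**What the plan says.** Objective 2a (Protocol 2.2) concerns participants with an IRN or an ECG app-AFib result and measures the proportion "reporting contact with a non-study healthcare provider at 15 and 60 days after study enrollment". The numerator in SAP 4.3 is those who "reported contact with a non-study healthcare provider at 15 (and separately at 60) days after study enrollment"; Protocol 10.3.2 gives the same estimator. The analysis set is the EEAS.

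On timing, Protocol 7.1 states: "A 15-day PRO will become available 15 days after enrollment, no later than END OF ENROLLMENT + 15". Protocol 7.8 gives the response period for both questionnaires: "the participant will have 30 days, up until END OF ENROLLMENT + 90, to complete them". Protocol 4.1 also sets the due date at 30 days from notification, with reminders.

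On Visit #2, Protocol 7.6 says: "It is expected that this visit will occur between 15-45 days after enrollment". At that visit the patch report is reviewed and, where there is AF, another arrhythmia or a non-urgent symptom needing evaluation, "the Study Telehealth Provider will direct the participant to their primary health care provider, or other health care provider" (Protocol 4.1).

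The topics listed in Protocol 7.8 include whether the participant followed up with a non-study provider. They include neither a date of contact nor a look-back limit. SAP 4.6 treats a questionnaire as missing only if there is no response.

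**The concern.** The label and the measurement do not match. What the plan collects is whether contact had occurred by the day the participant answered, and that day can be anywhere from day 15 to day 45. During the same period the study itself returns results and sends some participants to a provider. Someone with no contact by day 15, referred at Visit #2 on day 30, seen by a doctor on day 35 and answering on day 40 enters the numerator of the 15-day proportion.

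The reported figure then depends partly on how promptly people answer. Because referral follows patch findings, any inflation is likely to be greater in participants with AF or another arrhythmia, which could distort comparisons between groups. The change from 15 to 60 days is also hard to read when the interval between a participant's two answers is not fixed.

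**Working it through.** **Inputs.** Enrollment ends on day 180 and the study closes on day 270 (Protocol Table 1). The questionnaires open 15 and 60 days after each participant's enrollment (Protocol 7.1). The response period is 30 days (Protocol 4.1 and 7.8). Visit #2 is expected on days 15 to 45 (Protocol 7.6).

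**1. Check of the 30-day period against the plan's own figure.** The last participant enrolls on day 180, receives the 60-day questionnaire 60 days later and has 30 days to answer: 180 + 60 + 30 = 270. This reproduces the closing day in Table 1. Protocol 7.1 also says "All PROs will be due by end of study on END OF ENROLLMENT + 90", which read alone would let early enrollees answer much later, but 4.1 and 7.8 both set 30 days, so that limit is used here.

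**2. The 15-day questionnaire.** It opens on day 15 and closes on day 15 + 30 = 45. The expected Visit #2 period is days 15 to 45. The overlap is 30 of 30 days.

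**3. The 60-day questionnaire.** It opens on day 60 and closes on day 60 + 30 = 90. This lies wholly after the expected Visit #2 period, so only the date drifts.

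**4. Interval between a participant's two answers.** Shortest: 60 − 45 = 15 days. Longest: 90 − 15 = 75 days.

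**5. Direction of the error.** Having had contact is cumulative. For a participant who answers accurately, contact by the response date cannot be less than contact by day 15. The error among such responders is therefore upward or zero. Imputing non-responders from these answers would carry the error forward.

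**6. Size.** Among responders,

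inflation = (share answering late) × (share of those whose first contact fell between day 15 and the answer).

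The documents give neither share, so the values below are assumptions:

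| Share answering late | Share of those with first contact after day 15 | Inflation |
|---|---|---|
| 10% | 10% | 1 point |
| 25% | 20% | 5 points |
| 50% | 30% | 15 points |

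In the middle row, a true 30% would be reported as 35%.

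**The case against.** The strongest reply is that many participants will answer soon after the day-15 notification. Protocol 7.4.2 expects most patches back at about days 14 to 20, and extraction, technical reading and adjudication follow, so early answers will usually precede Visit #2. Reminders also favour prompt completion. This stands: a reader might infer that the questionnaire does not measure 15-day contact at all, and the documents do not support that. It measures it unreliably, to a degree that depends on an unknown distribution of response times.

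Second, the questionnaire itself is not reproduced. Protocol 7.8 lists topics only, and the instrument may already date the contact. This also stands, and the fix allows for it; the SAP would still need to say that the date is used.

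Third, a reader might take day 15 as the last point that shows response to the watch before the study intervenes. The documents do not support that either. Everyone in the EEAS has had Visit #1, a clinical evaluation whose summary may go to the participant's physician, and the expected patch-return dates imply that for most this came before day 15. Objective 2a does not claim to isolate the effect of the watch. Nor does the planned look at behavioral response to notifications in the 15-day questionnaire bear directly on 2a: Protocol 10.3.4 and SAP 4.3 place engagement with a provider in the 60-day one.

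Fourth, a reader might extend the Visit #2 problem to the 60-day result. That window opens after Visit #2 is expected to be over, so the extension fails.

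Finally, 2a is one descriptive secondary proportion in a study without hypotheses. That limits the stakes, but a figure reported as 15-day contact should still count contact by day 15.

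**Conclusion.** The point holds in a limited form. Followed as written, the plan counts first contacts made after day 15, up to day 45, as 15-day contacts, including those prompted by the Visit #2 referral. The 15-day proportion among accurate responders is biased upward or unchanged. The amount cannot be computed from the documents; the range of 1 to 15 points rests wholly on assumed shares. The 60-day proportion has date drift of up to 30 days and no comparable overlap with Visit #2. The conclusion assumes that the questionnaire contains no contact date or look-back limit beyond the topics listed, and that Visit #2 takes place when the protocol expects. It concerns the timing of contact and makes no claim that day 15 separates the effect of the watch from that of the study. A change before analysis is worthwhile because the direction of the error is known and the remedy is cheap.

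**What to change.** In both questionnaires, ask for the date of first contact with a non-study provider, or whether it occurred by day 15 or day 60. In SAP 4.3, count only contacts on or before day 15 for the first proportion and on or before day 60 for the second, whatever the response date. If the questionnaire already dates the contact, it is enough to state that this date defines the outcome.

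If the survey cannot be changed, keep the full 2a estimate but label it as contact by the date of response (days 15 to 45, and days 60 to 90). If completion times are recorded, which the documents do not say, show the 15-day result split by response before or after Visit #2. That split should be a sensitivity display only: it selects on speed of response and of patch processing, and it is not clean, because an urgent patch finding or the notice that the report is ready can prompt contact before Visit #2.

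The cost is one survey item and a short SAP amendment, with some recall error in the contact date. Sample size and visit schedule are unaffected.

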7.9 Data to be collected from HealthKit and Apple Watch

There will be two phases to HealthKit and Apple Watch data collection. Phase 1 will occur between the study start date and approximately January 2019. Phase 2 will occur from approximately January 2019 and later. Participants in each phase will consent to the specific data to be collected in each phase. If a participant begins participation in Phase 1 of the study and remains in the study when Phase 2 begins, the participant will be re-consented for Phase 2.

In Phase 1 of the study, no data will be collected from HealthKit or Apple Watch. In Phase 2 of the study, this study will collect participant data from the Apple Watch and iPhone, including heart rate tachograms, IRNs, and ECG app results. Data will include ECG waveform data from the ECG app. Data will be prospectively collected, beginning after consent and continuing until the end of study. In addition, we will retrospectively collect IRNs and ECG app classifications that were recorded within the 14 days prior to consent.

7.10 Time and Events Schedule

Evaluation	Screening and Eligibility	Consent and Enrollment	Study Visit #1	Study Visit #2	15- Day PRO	60-Day PRO
Inclusion/Exclusion Criteria	X					
Informed Consent		X				
Demographics/Medical History Questionnaire		X				
Health status		X				X
Experience with IRN feature and Apple Watch ECG app					X	
Ambulatory ECG Monitor – Introduction/Shipment			X			

This document contains information that is privileged or confidential and may not be disclosed unless such disclosure is required by applicable laws and regulations. The information in this document is the property of Apple Inc. and may not be reproduced, published, or disclosed to others without written authorization from Apple Inc.

Virtual Review of Medical History / Physical Symptoms			X			
Ambulatory ECG Monitor - Results Review				X		
Arrhythmia Recommendations for PCP referral				X		
Survey Completion					X	X

7.11 Participant Recontact

For participants who do not complete study procedures on time, study staff may contact the participant by email or phone to encourage timely completion of study procedures.

This document contains information that is privileged or confidential and may not be disclosed unless such disclosure is required by applicable laws and regulations. The information in this document is the property of Apple Inc. and may not be reproduced, published, or disclosed to others without written authorization from Apple Inc.

7.12 Participants that may be excluded from specific analyses

Participants may be excluded from some analyses for incomplete data or for various other reasons. The reasons may include:

1. Failure to contact Study Telehealth Provider within 30 days of enrollment.
2. Failure to be deemed eligible for ePatch wear due to emergent symptoms, determined at Study Visit #1.
3. Failure to return an ePatch within 45 days of enrollment.
4. Failure to begin wearing ePatch within 14 days of patch shipment
5. Failure to verify at Study Visit #1 that the participant had a cohort classification as either (1) Irregular Rhythm Notification, or status of (2) Afib or (3) Inconclusive via the ECG app (i.e., with at least 1 ECG recorded within the 14 days before study enrollment indicating classification of either AFib or Inconclusive, where the latter is defined as “Inconclusive,” “Heart Rate Over 120,” or “Heart Rate Under 50”)
6. Withdrawal from the study per Section 9.0

This document contains information that is privileged or confidential and may not be disclosed unless such disclosure is required by applicable laws and regulations. The information in this document is the property of Apple Inc. and may not be reproduced, published, or disclosed to others without written authorization from Apple Inc.

